## • Permanent impairment to a body structure or body function

Relationship of AE to the study: The relationship of the AE to the study devices or procedures will be classified as either:

- **Related**: The adverse event has a reasonable temporal relationship to the use of the device or the procedure and cannot reasonably be explained by known characteristics of the participant's clinical state or other therapies.
- Not Related: The adverse event is due to the underlying disease state or is due to concomitant medication or therapy not related to the use of the device.
- **Unknown**: If the adverse event cannot be determined to have a causal relationship, it will be classified as unknown.

Unanticipated: The sponsor is responsible for classifying AEs as anticipated or unanticipated according to the accepted regulatory definitions.

The PI and research team will be responsible for ensuring participants' safety daily and for the reporting of any SAEs and unanticipated AEs that are determined relevant to the devices or study procedures. For reportable events, the research team will follow applicable regulatory requirements to report the event to regulatory authorities and to the IRB immediately.

#### **Data and Safety Monitoring Plan**

Investigators and research staff will make every effort to maintain confidentiality. Once patients consent and are enrolled into the study they will be given a participant ID number that will be used to track and identify them for the remainder of study. Only those directly involved in the research will have access to the document matching the participant's name with participant ID number. Electronic data will be de-identified and stored on an encrypted and secured network drive which is only accessible to the research team. All paper files will be stored in a secured and

locked filing cabinet only accessible by research staff at [name] in the research office.

All study personnel will be responsible for knowing the protocol and adhering to the protocol. Study personnel will self-check and review the protocol frequently to ensure they know it very well. If a study team member is found to deviate from the protocol, the member will be warned and reminded of the protocol. If this occurs multiple times, the member will be removed from the study and the mistakes reported to the IRB. Changes to protocol will not be implemented until approved by IRB.

#### STUDY RISKS & BENEFITS

#### Potential Risks to Study Participants & Risk Mitigation

- 1. Potential Risk: Loss of confidentiality
  - Risk Mitigation: All reasonable barriers will be in place to protect against the potential loss of confidentiality:
    - Data will be de-identified and data collection tools used to collect participants data will use unique subject ID numbers for identification
    - ii. Only generic demographic variables (e.g., age, sex, race) needed to evaluate participant characteristics will be captured in data collection
    - iii. Study materials and data collection tools will be kept in secure, locked areas only accessible to research team
    - iv. Electronic spreadsheets will only be accessible to assigned authorized personnel and will be password protected
    - v. Imaging (e.g., CT scan) will only be accessible by PI and clinical staff, and will be de-identified and labeled with subject ID numbers before

- volumetric assessments are completed
- vi. Study records will be continually monitored by study coordinators to ensure all data is de-identified. Any oversights will be corrected and research team members will be notified.
- 2. Potential Risk: Harm from radiation exposure during weight-bearing CT scan
  - Risk Mitigation: All reasonable limitations and protections against potential
    adverse health effects that may be associated with radiation exposure will be in
    place:
    - Patients that are not able to complete the WBCT necessary for volumetric assessments will be excluded
    - ii. During the consent process, the research team and the participant will discuss and assess the participant's exposure history and determine if the potential risk is acceptable for that participant. The participant will be given the opportunity to decline to participate in the study and not undergo the WBCT without any loss of benefits to which the participant was otherwise entitled.
- 3. Potential Risk: Surgery and surgical device implantation risks including infection and foreign body reactions or sensitivities. Other specific adverse effects noted for the study devices include: osteomyelitis surrounding the TightRope, failure of the implant resulting in re-diastasis, and painful aseptic osteolysis related to the wear of the FiberWire (not noted for XP). The InternalBrace does not have any known increased risk beyond potential material sensitivity.
  - Risk Mitigation: All reasonable limitations and protections against potential

adverse health effects that may be associated with surgery and device implantation will be in place:

- The study doctor will complete standard of care evaluations to determine whether the patient is a good candidate for either of the TightRope fixation procedures.
- ii. During the consent process, the research team and the participant will discuss and assess the participant's history and determine if the potential risk of device or surgical related risks are acceptable for that participant. The participant will be given the opportunity to decline to participate in the study and not undergo the TightRope procedure without any loss of benefits to which the participant was otherwise entitled.
- iii. Standard of care procedures will be followed during the procedure to minimize the risk of infection and device failure.
- iv. Post-operative directives and follow-ups will follow standard of care to minimize device failure, and any adverse effect throughout study timeline will be reported as required and outlined above.
- 4. Potential Risk: Psychosocial stress or discomfort as a result of filling out the questionnaires
  - Risk Mitigation: All reasonable procedures will be in place to protect against
    psychosocial stress or discomfort related to questionnaires, and patients will be
    informed that participation is voluntary and that they may cease participation at
    any time.

### **Potential Benefits to Participation**

There are no known benefits to the participants for participating in the study. However, it is possible that their involvement may advance knowledge and evidence regarding best practices for caring for ankle injuries that disrupt the syndesmosis.

#### STATISTICAL ANALYSIS PLAN

Significance will be set a priori at P = 0.05. All statistical analyses will be conducted using IBM SPSS Statistics, Version 28 (IBM Corporation, Armonk, NY). Descriptive analysis will be performed to describe participant characteristics and independent t-tests will be used to determine differences in pre-operative characteristics and outcomes between groups. In order to compare the 3D syndesmotic volume between groups, the volume ratio will first be calculated for each patient by dividing the syndesmotic volume of the contralateral uninjured ankle by the syndesmotic volume of the operative ankle. Separate t-tests will then be performed to determine whether there are differences between the volumetric ratios, FAOS scores, and SF-36 scores between groups at each collection time point. Pearson-product moment correlations will be conducted to explore relationships between the volumetric ratios and each PRO (FAOS and SF-36) at both 6-weeks and 3-months. Pearson correlation coefficients (r) will be interpreted as (negligible < 0.3, low = 0.3-0.49, moderate = 0.5-0.69, high = 0.7-0.89, very high = 0.9-1.0).

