#### **Design**

We will use a prospective, two-arm, single-blind, randomized study design to conduct our pilot study. After informed consent, twenty patients will be randomized evenly into a traditional TightRope fixation group or a TightRope fixation with an AITFL augmentation group upon enrollment into the study. As this is a pilot study with a small sample size, block randomization will be used to reduce the risk of unequal group sizes between groups. A researcher who will not otherwise be involved in patient interactions will serve as the randomization coordinator for this trial. They will prepare a randomization schedule using the freely accessible tools available at www.randomization.com. The sequence generator uses block randomization procedures based on the number of interventions and patients needed in each block and creates a schedule based on the patient ID number. Due to the potential emergent nature of injuries involved in this study and a short time between enrollment and surgery, the surgeon may need to acquire the group allocation shortly after enrolling patients to be able to prepare for the surgery and so the schedule will be converted to a Google Document that can then be accessed by the surgeon/PI to reveal the intervention allocation. Since pre-operative and post-operative instructions are the same regardless of the procedure, the participants will be blinded to their intervention group until the completion of the study period.

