#### 2. STUDY PROCEDURES

Prospective patients will enter the clinic or hospital associated with the study doctor seeking care after ankle trauma. Patient will be moved through clinic/hospital workflow as normal. Once the patient elects to undergo syndesmotic stabilization surgery and is over 18 years of age, study protocol will be triggered as follows:

1. The study doctor will do an initial clinical screening for open fractures or fractures that would require a posterolateral approach during his examination, and if present, the patient will be excluded. If patients are not excluded at this point, the study doctor or another

member of the research team will enter the room and work through the informed consent process with the goal of obtaining the consent. Patient will have ample opportunity to read through documents to their desire. Patient will be asked if they are literate and speak English comfortably and excluded if they do not answer yes to both questions.

- 2. Once the consent is signed, a research team member will review patient's medical history for presence of other exclusion factors: previous ankle surgery, or any contralateral foot or ankle injury. If any exclusion factor is present, consent documents will be shredded.
- 3. If no exclusion factors are present at this point, the following will occur:
  - a. The patient will be issued a participant ID number and will complete the preoperative patient-reported outcomes (PROs) related to their perceived ankle function (The Foot and Ankle Outcome Score) and generic health status (SF-36). These will be administered by a research team member by using either paper format, or a tablet computer through a survey administration software called Surgical Outcome System (SOS).
  - b. The participant ID will be used by the study doctor to verify their randomized group allocation schedule generated by block randomization procedures described above and will be scheduled for their respective surgery.
- 4. Patient will follow typical pre-operative procedures. During the procedure, the patients will be in a supine position so that the fibula and the lateral ankle ligaments can be exposed. The integrity of the AITFL will be examined by the study doctor, and if disrupted the participant will be included in the study and will undergo either the traditional TightRope fixation procedure or the double stabilization procedure (TightRope fixation plus *Internal*Brace augmentation) as assigned and performed by the

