- study doctor. If AITFL disruption is not confirmed at this point, the patient will be excluded from the study; however, will still undergo the appropriate stabilization procedures necessary for treating their traumatic injury. If patients are excluded at this point, they will be informed post-operatively, and all study documents will be shredded.
- 5. If participants are not excluded and are assigned to the traditional TightRope fixation group: the fibular fracture will be stabilized with fixation and the plate will be applied laterally to the fibula. The syndesmosis is directly reduced and held in a stable position with the TightRope device. The syndesmosis is then restressed and examined to ensure that it is stable and reduced.
- 6. If participant is not excluded and is assigned to the TightRope fixation plus *Internal*Brace augmentation group: the FiberTape portion of the *Internal*Brace will be threaded through the distal fibular plate which will then be applied. The fibular fracture will be stabilized with fixation and the plate applied laterally to the fibula. The syndesmosis will be directly reduced and held in a stable position with the TightRope device. A 3.4 mm drill and 4.75 mm tap are used to make a small hole in the distal tibia at the anatomic origin of the anterior inferior tibiofibular ligament. A 4.75 mm SwiveLock anchor is then used to set the tension of the AITFL repair over the top of the torn AITFL ligament. The syndesmosis is then restressed and examined to ensure that it is stable and reduced.
- 7. Pre-operative PRO data for all eligible participants will be entered into a spreadsheet by a research team member along with basic demographic information (age, biological sex, height, weight, race), involved side (right or left ankle), type of procedure (traditional or traditional plus augmentation), and any relevant surgical notes.

- 8. All participants will be given the same post-operative directives regarding treatments and care which includes being non-weightbearing and immobilized for the first two weeks after surgery. At this point, the patients will begin a physical therapy program incorporating passive modalities and gentle range-of-motion exercises. Patients will remain non-weightbearing in a post-operative cam boot for the next 4-6 weeks.

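### Pre-operative FAOS and SF-36 scores are collected and tested between arms but not used as covariates, which may cost precision on the secondary outcomes

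*Combined protocol and SAP*

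**What the plan says.** On baseline, the STATISTICAL ANALYSIS PLAN section says two things in one sentence: "Descriptive analysis will be performed to describe participant characteristics", and "independent t-tests will be used to determine differences in pre-operative characteristics and outcomes between groups". It names no other between-group test for baseline data. It does not list which characteristics are tested, and it attaches no action to any result.

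On follow-up, the same section says "Separate t-tests will then be performed to determine whether there are differences between the volumetric ratios, FAOS scores, and SF-36 scores between groups", at every collection time point. No covariate is mentioned. The threshold is given as "Significance will be set a priori at P = 0.05", with no statement of one- or two-sided testing.

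On the data available:
- Section 2 (STUDY PROCEDURES), step 3a: before surgery each patient "will complete the preoperative patient-reported outcomes (PROs) related to their perceived ankle function (The Foot and Ankle Outcome Score) and generic health status (SF-36". Section 3 gives five FAOS subscales and two SF-36 summary scores (PCS and MCS), so seven scores have a pre-operative value.
- Section 2, step 7: the spreadsheet holds "basic demographic information (age, biological sex, height, weight, race), involved side (right or left ankle", among other items.
- Section 2, step 9: weight-bearing CT is done at 6 weeks and 3 months only. FAOS and SF-36 are thus the only outcomes measured before surgery.
- Design: "twenty patients will be randomized evenly into a traditional TightRope fixation group or a TightRope fixation with an AITFL augmentation group", and "block randomization will be used to reduce the risk of unequal group sizes between groups".

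**The concern.** A pre-operative score on the same scale is the natural covariate for a follow-up score. Here it is obtained from each patient, compared between arms, and then dropped. With so few patients, chance differences in pre-operative scores can be sizeable, and an unadjusted follow-up comparison carries part of them. At stake is the precision of the answer to the first secondary objective, on patient-reported ankle function and general health.

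The baseline tests themselves do little. Under randomisation any baseline difference is due to chance, so the test answers a question whose answer is known. Six items of demographics and side are recorded, and three of them (sex, race, side) are categorical, yet only a t-test is named.

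**Working it through.** The documents contain no sample size calculation, SD or correlation, so there is no figure of the plan to reproduce.

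**Inputs.** N = 20, 10 per arm (Design), all assumed analysed; alpha 0.05 (SAP), taken as two-sided; correlation ρ between pre- and post-operative score, assumed 0 to 0.7; true difference of 1 SD, assumed for illustration.

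**1. Chance imbalance.** The difference in mean pre-operative score between arms has SD √(2/10) = 0.45 score SDs. It exceeds 0.5 SD in either direction in about 26% of randomisations (normal approximation, 0.5/0.447 = 1.12). It enters the follow-up difference in proportion to ρ: an imbalance of 0.5 SD at ρ = 0.5 shifts the follow-up difference by 0.5 × 0.5 = 0.25 SD.

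**2. Variance under ANCOVA relative to the t-test.** Factor = (1 − ρ²)(1 + 1/(N − 4)) = (1 − ρ²)(17/16). The second term is the price of estimating the slope. Break-even is where the factor equals 1: ρ² = 1 − 16/17 = 1/17, so ρ ≈ 0.24.

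**3. Power and detectable difference** (noncentral t; 18 df for the t-test, 17 for ANCOVA):

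| Analysis | Variance factor | Power for 1 SD | Difference detectable with 80% power |
|---|---|---|---|
| t-test | 1 | 56% | 1.32 SD |
| ANCOVA, ρ = 0 | 1.0625 → 1.06 | 53% | 1.37 SD |
| ANCOVA, ρ = 0.3 | 0.91 × 1.0625 = 0.97 | 57% | 1.31 SD |
| ANCOVA, ρ = 0.5 | 0.75 × 1.0625 = 0.80 | 66% | 1.19 SD |
| ANCOVA, ρ = 0.7 | 0.51 × 1.0625 = 0.54 | 82% | 0.98 SD |

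The worst case costs about 3 points of power. At ρ = 0.7 the gain is about 26 points.

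**4. The t-test on a binary item (sex, side).** Enumerating all 11 × 11 outcomes for 10 per arm, the type I error is 0.9%, 3.0%, 3.7%, 4.0% and 4.2% at prevalence 0.1, 0.2, 0.3, 0.4 and 0.5. Given the observed total (2 to 10 of 20), it runs from 0% to 8.7%. For 8/10 against 3/10, P is 0.024 by t-test, 0.025 by uncorrected chi-square and 0.070 by Fisher's exact test. The t-test is approximate and behaves like the uncorrected chi-square.

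**5. The t-test on race.** Take an invented three-category split, A/B/C = 6/3/1 in one arm and 6/0/4 in the other.
- Codes A=1, B=2, C=3: means 1.5 and 1.8, P = 0.46.
- Codes A=1, B=3, C=2: means 1.7 and 1.4, P = 0.39.
- Codes A=2, B=1, C=3: means 1.8 and 2.4, P = 0.032.

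The data are the same each time; only the labels change.

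**6. Chance findings.** The seven scores alone give 1 − 0.95⁷ = 30% probability of at least one P < 0.05. With all six recorded items added, 1 − 0.95¹³ = 49%. Both figures assume independent tests, which is unlikely for related scales, so they are only a guide.

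**The case against.** The case for leaving the plan alone has four parts.

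- **The unadjusted t-tests are sound.** Over the randomisation they are unbiased and hold their error rate. This stands. A reader might infer that chance imbalance biases the follow-up comparisons; the randomised design does not support that.
- **The gain may be nil.** Pre-operative scores are taken after acute trauma and may say little about function months later. Below ρ of about 0.24, adjustment slightly increases the variance. This stands as a limit on the benefit, not as a reason against adjustment, since the loss is capped near 6%.
- **The primary outcome is untouched.** It has no pre-operative measurement. This stands in full.
- **The SAP may not intend t-tests on sex, race or side.** The tested characteristics are not listed, and the same sentence plans a description of participant characteristics. The confidentiality item under STUDY RISKS & BENEFITS gives age, sex and race as examples of the variables needed for exactly those participant characteristics. So the categorical items may be meant for description only. What remains is an ambiguity: the t-test clause makes no exception, and no categorical test is named.

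A reader might also infer that the trial will report invalid baseline P values for all three categorical items. The documents do not support that. They do not say that these items are tested; for sex and side the t-test would be approximate with overall error below 5%; and only race with three or more categories would give a meaningless P value. The documents do not give the race categories.

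**Conclusion.** The plan leaves available information unused in the FAOS and SF-36 comparisons. This is a possible loss of precision on secondary outcomes, not an error of validity. Its size depends on a correlation that the documents do not give: from a 6% variance penalty for adjusting (ρ = 0) to a 46% reduction (ρ = 0.7), with break-even near 0.24. The figures assume 10 analysed patients per arm, two-sided testing and a linear relation between pre- and post-operative scores.

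The baseline testing is a lesser matter. No baseline P value enters a treatment comparison, so no efficacy conclusion depends on it. Nor does the SAP plan to declare the arms comparable or imbalanced on the strength of these tests, although a reader of the results might do so. The whole point is a cheap improvement, confined to the secondary outcomes.

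**What to change.** Two sentences of the STATISTICAL ANALYSIS PLAN section need to change together. If only the baseline sentence is edited, the later one would still prescribe t-tests for FAOS and SF-36.

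1. Baseline sentence, suggested text: *Pre-operative characteristics and scores will be summarised by arm (mean and SD, or counts) without significance tests.*
2. Follow-up sentence, suggested text: *The volumetric ratios will be compared between arms by t-test at 6 weeks and 3 months. Each FAOS subscale and the SF-36 PCS and MCS will be compared between arms at each follow-up by ANCOVA with the pre-operative score of the same scale as covariate, reporting the adjusted mean difference and 95% CI.*

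The first change also removes the question of which test suits race, sex and side.

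The cost is wording only: no new data, visits or patients. The statistical downside is one degree of freedom and about 6% more variance if the pre-operative score turns out to be unrelated to outcome. The change should be made before outcomes are compared by arm.

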## 1. BACKGROUND, OBJECTIVES, & STUDY DESIGN

Ankle syndesmosis disruption due to ankle trauma is associated with significant pain and disability.  Surgical stabilization procedures typically involve an internal fixation of the distal tibiofibular joint to restore the spatial relationship of the bony structures. Rigid fixation has traditionally been the technique of choice for stabilizing the syndesmosis; however, dynamic fixation options like the TightRope® system (Arthrex®, Naples, United States) have more recently demonstrated some advantage over rigid screw fixation techniques as they attempt to mimic the dynamic nature of the syndesmosis.  Tightrope or flexible fixation is still a non-anatomic reduction and stabilization technique and as such is only an approximation of the syndesmotic ligaments.

Anterior inferior tibiofibular ligament (AITFL) augmentation techniques using nonabsorbable suture materials (*Internal*Brace, Arthrex®, Naples, United States) have been used to supplement syndesmotic fixation in order to more accurately reconstruct the syndesmosis and restore native biomechanics.  Clinical research assessing the use of the *Internal*Brace as an additional stabilization method is lacking and the minimum required stability to achieve successful clinical and patient-reported outcomes remains unclear.

The primary objective of this study is to evaluate the quality of syndesmotic reduction as determined by weight bearing 3-D relative volumetric ratio between ankles in patients undergoing syndesmotic stabilization with and without an *Internal*Brace augmented repair of the AITFL to determine if the technique influences the reduction and postoperative stability of the syndesmosis. This will be compared at both 6-weeks and 3-months post-operation. Our

secondary objectives are 1) to determine whether the addition of the *Internal*Brace augmentation to the traditional TightRope fixation procedure improves short- and long-term patient-reported ankle function and generic health ratings and 2) to explore relationships between syndesmotic volume and patient-reported outcomes across groups.

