#### 3. OUTCOMES & DATA

## **Primary Outcomes**

3D Syndesmotic Volume: Volumetric assessment of the distal syndesmosis will be performed with the WBCT using the CubeView software (CurveBeam, Warrington, PA). The software can calculate 3D volume amounts using cross-sectional imaging.

Measurements will start from the joint line and extend proximally, and will be performed by research staff blinded to the surgical procedure and trained by the study doctor.

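### The primary t-test compares mean volume ratios, but the plan names no target of 1, no worse direction and no distance from 1, so a difference need not mean better reduction

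*Combined protocol and SAP*

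**What the plan says.** Section 1 (Background, Objectives, & Study Design) gives the primary objective as "to evaluate the quality of syndesmotic reduction as determined by weight bearing 3-D relative volumetric ratio between ankles", and closes it with a second, non-directional clause: "to determine if the technique influences the reduction and postoperative stability of the syndesmosis". The same section says that augmentation has been used "in order to more accurately reconstruct the syndesmosis and restore native biomechanics".

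Section 3, Primary Outcomes, describes only the measurement: "Volumetric assessment of the distal syndesmosis will be performed with the WBCT using the CubeView software". It contains no ratio, reference value or threshold for malreduction.

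The Statistical Analysis Plan defines the ratio by "dividing the syndesmotic volume of the contralateral uninjured ankle by the syndesmotic volume of the operative ankle", then plans separate t-tests for a difference between groups at each time point, and Pearson correlations of the same ratio with the FAOS and SF-36 at 6 weeks and 3 months. No section states that a ratio of 1 is the goal, whether values above or below 1 are worse, or how far from 1 an ankle lies.

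**The concern.** Quality of reduction, judged against the patient's own uninjured ankle, means closeness to a ratio of 1. The planned test asks something else: whether the mean ratio is higher in one arm. A mean ratio can differ between two arms that are equally far from 1 on opposite sides. It can also agree between two arms when one is tightly clustered at 1 and the other widely scattered around it.

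The same difference can favour either arm. Means of 0.85 and 1.00, or of 1.00 and 1.15, differ by 0.15 in both cases; the higher arm is the more accurate in the first pair and the less accurate in the second. Without a written rule, the reading would be chosen after the data are seen. The exploratory correlations share the gap: if patients do worse the further they are from 1 in either direction, a straight-line correlation with the signed ratio can miss it.

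**Working it through.** **Inputs from the documents.** Twenty patients randomised evenly, so 10 per arm (Section 1, Design); significance level 0.05 (Statistical Analysis Plan), taken as two-sided because sidedness is not stated; the ratio R = contralateral volume / operative volume. The documents give no SD, effect size or power, so there is no figure to reproduce, and every mean and SD below is an assumption.

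**Direction and asymmetry of R.** An operative volume 20% too large gives R = 1/1.2 = 0.83; one 20% too small gives R = 1/0.8 = 1.25. So R below 1 means a larger operative-side volume (widening). Equal percentage errors are not equally far from 1 (0.17 against 0.25), and they largely cancel in a mean: (0.83 + 1.25)/2 = 1.04. The log scale treats inverse ratios evenly. Let x = ln(operative/contralateral), so R = exp(−x), the target is x = 0, and distance from the target is |x|.

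**Mean distance.** For x normal with mean m and SD s,

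E|x| = s·√(2/π)·exp(−m²/2s²) + m·[1 − 2Φ(−m/s)].

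For m = ±0.05, s = 0.10: 0.0798 × 0.8825 + 0.05 × 0.383 = 0.0704 + 0.0191 = 0.090 in both arms. For m = 0: 0.798 × 0.10 = 0.080 and 0.798 × 0.20 = 0.160. For m = 0.10, s = 0.10: 0.0484 + 0.0683 = 0.117.

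**Simulation.** 100,000 trials per row; planned = Student t-test on R; distance = Welch test on |x|. Entries are the share of trials significant at 0.05.

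| Assumed arms (mean of x; SD) | True mean distance | Planned | Distance |
|---|---|---|---|
| −0.025 vs 0.025; 0.10 | equal | 18% | 5% |
| −0.05 vs 0.05; 0.10 | equal (0.090) | 56% | 5% |
| −0.05 vs 0.05; 0.15 | equal | 29% | 5% |
| 0 vs 0; 0.10 vs 0.15 | 0.080 vs 0.120 | 5% | 16% |
| 0 vs 0; 0.10 vs 0.20 | 0.080 vs 0.160 | 5% | 38% |
| 0 vs 0.10; 0.10 | 0.080 vs 0.117 | 56% | 18% |
| 0.10 vs 0.20; 0.10 | 0.117 vs 0.202 | 56% | 52% |
| 0.05 vs 0.15; 0.05 | 0.058 vs 0.150 | 99% | 99% |

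In the first three rows the arms are equally accurate, yet the planned test often rejects. In the next two, one arm is truly more accurate and the planned test stays near its nominal level. In the last three the planned test points to the right arm, and in the row 0 vs 0.10 it does so far more often than the distance test.

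If every error is widening (gamma, shape 4, means 0.10 and 0.20), then |x| = x. The signed and distance tests on the log scale are identical at 79%, and the planned test gives 81%.

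**Correlations.** With n = 20, SD 0.10, and a patient-reported score assumed to follow |x| at r = −0.6, the share significant for R against |x| is 13% vs 82% at mean error 0, 65% vs 83% at 0.10, and 82% vs 84% at 0.20.

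**The case against.** The strongest reply is that the plan largely answers the question it states. The last clause of the objective asks only whether technique has an influence, and a two-sample t-test on the ratio addresses that. Quality is said to be determined by the ratio, and dividing by the uninjured side makes 1 the implicit reference. On this view only a sentence of interpretation is missing. This stands for the second clause of the objective. It does not stand for the first, because the test does not use the implicit reference, and arm means alone cannot show a difference in spread.

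Second, the misleading cases may not arise. The only volume error that the documents name is widening ("failure of the implant resulting in re-diastasis"), and in both arms "The syndesmosis is then restressed and examined to ensure that it is stable and reduced". That is fair: how often errors straddle 1 is unknown. A reader might go further and infer that augmentation over-tightens the joint, since "A 4.75 mm SwiveLock anchor is then used to set the tension of the AITFL repair" applies in one arm only. The documents do not say so; the risk section reports no known added risk of the augmentation device beyond material sensitivity. Over-compression is an inference, and the point does not need it, because unequal spread is enough.

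Third, a reader might take the 56% as a false-positive rate and call the planned test invalid. It is neither: in that scenario the mean ratios really differ and the test is right to reject. It becomes an error only if reported as better reduction, and the plan contains no such rule.

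Fourth, this is a small pilot, and the distance measure can lose power (18% against 56% in the row 0 vs 0.10). Both are true. They argue for keeping the signed comparison beside the distance measure, not for leaving quality undefined.

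**Conclusion.** The concern holds in a limited form. The t-test is a sound test of a difference in mean ratio, but the primary objective is quality of reduction, and no section connects the two through a target, a direction or a distance from 1. This mismatch can be read from the documents and depends on no assumed value.

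Its practical size does depend on assumptions. With 10 per arm, the planned test is significant in 18% to 56% of trials with equally accurate arms on opposite sides of 1, and in about 5% when accuracy differs only through spread. When errors are one-sided it ranks the arms correctly and little is lost. The documents do not show which situation applies. This is a cheap improvement to the plan and does not make the trial's comparison invalid.

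**What to change.** In the Statistical Analysis Plan:

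1. State that a ratio of 1 is the target, and that a contralateral/operative ratio below 1 means a larger operative-side volume (widening).
2. Keep the signed comparison, preferably as ln(operative/contralateral), for whether technique influences the reduction.
3. Pre-specify |ln(operative/contralateral)| as the measure of reduction quality. Give its between-arm difference with a 95% CI at 6 weeks and 3 months (Welch or rank test), plus arm means, SDs and individual values.
4. Base any statement of better reduction on |ln ratio| only. Report a signed difference without a difference in |ln ratio| as a difference in mean direction. Which arm's mean lies nearer to 1 is not a substitute: an arm with log mean 0 and SD 0.15 has mean distance 0.120, worse than the 0.101 of an arm with mean 0.10 and SD 0.05.
5. Add |ln ratio| to the exploratory correlations.

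The cost is wording and one more analysis per time point on the same scans. If the arms do not differ at all, the chance that at least one of the two measures is significant is about 9% per time point, and higher over two visits. Power for |ln ratio| is lower when errors straddle 1: in the case 0 vs 0.10, SD 0.10, about 41% of trials would show a signed difference only and be reported as direction, although one arm is truly closer. With 20 patients the results should be labelled exploratory.
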